4.4 Early Withdrawal of Subjects

4.4.1 When and How to Withdraw Subjects

Subjects will be withdrawn if they develop serious medical illness during the study, defined as an event determined to be grade 3 or higher, i.e., severe or life-threatening. The exception is a single event of syncope if felt by the PI to be vasovagal in etiology and related to catheter placement or venipuncture. Vasovagal syncope in response to blood drawing and IV placement is common and does not warrant study withdrawal if the subject's loss of consciousness is brief (i.e., less than 5 minutes) and does not require further medical attention.

4.4.2 Data Collection and Follow-up for Withdrawn Subjects

Data collected prior to withdrawal will be analyzed if possible. No data collection will take place after withdrawal in subjects who drop out of the study.

5 Study Drug

5.1 Description

^{11}C -PBR28 is a PET radioligand that binds to the 18 kDa translocator protein. ^{11}C -PBR28 will be administered at tracer doses and is not expected to have a pharmacological effect.

5.2 Treatment Regimen

N/A

5.3 Method for Assigning Subjects to Treatment Groups

N/A

5.4 Preparation and Administration of Study Drug

^{11}C -PBR28 will be synthesized and administered by the CUMC PET Department. Injection will be administered at a target imaging dose of up to 20 mCi (740 MBq).

Calculation of activity to be injected will be performed by a qualified radiopharmacist in the CUMC PET department.

5.5 Subject Compliance Monitoring

N/A

5.6 Prior and Concomitant Therapy

Subjects will not be included if they are currently taking anticoagulants such as warfarin. Antiplatelet drugs such as aspirin are allowed.

5.7 Packaging

N/A

5.8 Blinding of Study Drug

N/A

5.9 Receiving, Storage, Dispensing and Return

5.9.1 Receipt of Drug Supplies

Upon receipt of the of the study treatment supplies, the CUMC PET Center staff will perform an inventory and a drug receipt log will be filled out and signed by the person accepting the shipment. Any damaged or unusable study drug in a given shipment (active drug or comparator) will be documented in the study files.

5.9.2 Storage

N/A

5.9.3 Dispensing of Study Drug

^{11}C -PBR28 will be administered the same day of synthesis.

5.9.4 Return or Destruction of Study Drug

Any unused radiopharmaceutical will be on site and documented in the study files.

6 Study Procedures

This study will involve up to 3 outpatient visits. See schedule below.

At the first screening visit, subjects will sign informed consent, undergo history and physical and neurological examination, and have blood drawn for routine safety laboratories. Menopause (defined as absence of menses for at least one year) or history of hysterectomy and/or tubal ligation will be confirmed by medical history to exclude women of child-bearing potential. Blood will also be drawn for TSPO, ApoE and GBA genotyping if not previously performed in another study.

Brain MRI will take place at the Neurological Institute Neuro MRI Center on 3T Philips scanner. MRI will be performed to rule out intracranial disease other than PDD or DLB, and for coregistration with the PET images for analysis. An additional screening visit is required for brain MRI; however, this may be performed on the same day as the first screening visit is scheduling allows. Up to 2 screening visits are therefore anticipated. However, additional visits may be necessary if certain tests must be scheduled on different days due to scheduling. If subjects require a sedative for the MRI (e.g., because of claustrophobia), they may receive a onetime dose of lorazepam (0.5 - 1 mg orally) or equivalent dose of an alternative benzodiazepine prior to the MRI. Side effects of anti-anxiety medications may include prolonged sedation (usually less than 8 hours), lightheadedness, motor incoordination, difficulties with balance, or confusion. These effects are temporary and go away after several hours. Subjects will be instructed not to drive, handle machinery, or drink alcohol until the next day. Subjects who receive an anti-anxiety medication will be instructed to bring a companion to the MRI study

CONFIDENTIAL

This material is the property of Columbia University Medical Center. Do not disclose or use except as authorized in writing by the study sponsor

visit, and will be accompanied by a member of the study staff during the MRI. The PI will be available in the event of an adverse event during the MRI.

One study visit will be required for the ^{11}C -PBR28 PET scan. At the PET scan visit, one IV catheter will be placed by a qualified clinician for purposes of radioligand injection. After performing an Allen test to ensure ulnar perfusion to the hand, a catheter will be placed in the radial artery by a qualified clinician. After a CT attenuation scan, up to 20 mCi ^{11}C -PBR28 will be injected via the IV. The emission scan will last 90 minutes, during which members of the study team will draw arterial blood samples.

^{11}C -PBR28 PET scans must be completed within 12 months of the brain MRI. Other screening procedures must be done within 60 days prior to the PET scan.

Study Procedures	Screen ^a	Study ^b
	Day -60 to 1	Visit 1
Informed consent	X	
Medical history	X	
Inclusion/exclusion criteria	X	X
Blood draw for genetic tests	X	
MRI	X	
^{11}C -PBR28 PET		X
Laboratory determinations	X	
Neurological examination	X	
Vital signs	X	
Height and weight	X	
Adverse events	X	X

CONFIDENTIAL

This material is the property of Columbia University Medical Center. Do not disclose or use except as authorized in writing by the study sponsor

7 Statistical Plan

7.1 Sample Size Determination

This study is intended to generate pilot data as ^{11}C -PBR28 PET imaging has not previously been performed in patients with diffuse Lewy body disease. Therefore, preliminary data to accurately power this study does not exist. However, our previous study using ^{11}C -PBR28 in patients with Alzheimer's disease (a different neurodegenerative disease) showed effect size of 1.5 in brain regions with largest difference between patients and controls. If a similar effect size is seen in patients with diffuse Lewy body disease then we would expect statistically significant differences with sample size of $n = 8$.

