Objectives	
The primary objective is to generate pilot data in patients with DLBD. The aims are:
 
1. Determine feasibility of performing ¹¹C-PBR28 PET in patients with DLBD.2. Determine effect size of ¹¹C-PBR28 binding in patients with DLBD vs. controls. The exploratory aims are: 
1. Identify potential reference regions for ¹¹C-PBR28 binding in patients with DLBD.2. Determine if ¹¹C-PBR28 binding correlates with cognitive impairment and Parkinsonism in patients with DLBD.
Number of Subjects	
Target enrollment is 8 patients and 8 controls.
 
Target accrual is 4 patients and 4 controls.

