Statistical Methodology	
Primary outcome PET images will be analyzed using 1) the two-tissue kinetic model to calculate total distribution volume, corrected for free fraction of radioligand in plasma (V_T/f_P), and 2) the cerebellum as a pseudo-reference region to calculate standardized uptake value ratios (SUVR). Effect size will be calculated for different regions as the difference in means (DLBD vs. controls) divided by the standard deviation.
 
Secondary outcomes Coefficient of variation (%COV = standard deviation / mean) will be calculated for controls and patients with DLBD for both V_T/f_P and SUVR data. SUVR values will be calculated using cerebellum as reference regions. Additional reference regions will be explored. Correlation coefficients will be computed to look for correlation between ^{11}C-PBR28 binding (V_T/f_P and SUVR) and clinical severity. Severity will be measured using CDR-sum of boxes, MoCA score, and UPDRS. We will also look for correlations between ^{11}C-PBR28 binding and atrophy, as determined using ROI volumes derived from MRI data.
 
Sample size determination This is a Phase 2 pilot study to determine feasibility and preliminary data for a larger study. Therefore, the proposed sample size is not expected to provide enough statistical power to see significant group differences.

CONFIDENTIAL

This material is the property of Columbia University Medical Center. Do not disclose or use except as authorized in writing by the study sponsor

1 Introduction

This document is a protocol for a human research study. This study is to be conducted according to US and international standards of Good Clinical Practice (FDA Title 21 part 312 and International Conference on Harmonization guidelines), applicable government regulations and Institutional research policies and procedures.

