^{11}C -(*R*)-PK 11195 has low specific-to-nonspecific binding[25] which could confound accurate quantification of TSPO density. The second generation TSPO radioligand ^{11}C -PBR28 has greater specific-to-nonspecific binding than ^{11}C -(*R*)-PK 11195 in monkey brain[25] and has been used to detect neuroimmune activation in stroke, schizophrenia, and epilepsy[26-28]. Therefore, ^{11}C -PBR28 PET imaging is expected to detect inflammatory changes in DLBD and may be useful for monitoring disease progression and response to novel treatments. Because the relationship between inflammation and the clinical symptoms exhibited in DLBD remains unknown, there is a critical need to determine the relationship between inflammation and DLBD to increase knowledge about the mechanisms underlying the disease and help develop antiinflammatory treatments as disease-modifying therapy for this presently incurable disorder.

One limitation of ^{11}C -PBR28, shared by all tested second generation TSPO radioligands, is differential affinity caused by the rs6971 single nucleotide polymorphism on the TSPO gene[29]. Statistical correction for TSPO genotype allows inclusion of individual heterozygous for the polymorphism; however, homozygotes have negligible binding with ^{11}C -PBR28 and must be excluded from analysis[27].

The primary research objective is to generate pilot data in patients with DLBD to more effectively design an R01 application to comprehensively study the relationship between inflammation and DLBD. The aims are to:

1. Determine feasibility of performing ^{11}C -PBR28 PET in patients with DLBD.
2. Determine effect size of ^{11}C -PBR28 binding in patients with DLBD vs. controls. The exploratory aims are:
 1. Identify potential reference regions for ^{11}C -PBR28 binding in patients with DLBD.
 2. Determine if ^{11}C -PBR28 binding correlates with cognitive impairment and Parkinsonism in patients with DLBD.

1.2 *Investigational Agent*

^{11}C -PBR28 is a PET radioligand that binds to the 18 kDa translocator protein (TSPO), a marker of inflammation. ^{11}C -PBR28 has previously been administered in humans.

This radioligand will be administered in tracer doses. ^{11}C -PBR28 will be administered at activity of up to 20 mCi per injection.

1.3 *Preclinical Data*

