1.5 Dose Rationale and Risk/Benefits

Based on prior human experience and human dosimetry data, we expect the proposed injected activity of ^{11}C -PBR28 (up to 20 mCi) to be safe without expected toxicity.

2 Study Objectives

Primary objectives

- 1). Determine feasibility of performing ^{11}C -PBR28 PET in patients with DLBD.
- 2). Determine effect size of ^{11}C -PBR28 binding in patients with DLBD vs. controls.

Our hypothesis is that ^{11}C -PBR28 binding will be greater in DLBD patients than controls, with largest differences in temporal and limbic regions.

Secondary objectives

- 1). Identify potential reference regions for ^{11}C -PBR28 binding in patients with DLBD.

Our hypothesis is that correcting cortical ^{11}C -PBR28 binding to that in the cerebellum, a region typically spared from pathology early in DLBD, will reduce intra-subject variance, avoid need for arterial catheterization, and improve sensitivity for detecting differences between DLBD patients and controls. We will also explore other potential reference regions such as cortical white matter.

- 2). Determine if ^{11}C -PBR28 binding correlates with cognitive impairment and Parkinsonism in patients with DLBD.

We postulate that ^{11}C -PBR28 binding will correlate with clinical severity (cognitive impairment and Parkinsonism) and the amount of atrophy on MRI.

3 Study Design

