3.1 General Design

Subject selection. Patients and controls will be recruited from the ADRC, CUMC clinics, and direct referrals. Target accrual is $n = 4$ completers in each group (DLBD and controls). ADRC subjects who have already undergone GBA and ApoE genotyping through ADRC participation will be preferentially enrolled. If possible, only previously-determined GBA mutation carriers will be included. However, if not enough GBA mutation carriers are recruited to meet target enrollment we will also enroll GBA non-carriers who are also known ApoE4 noncarriers. This strategy is designed to reduce the inclusion of patients with co-existent AD-related tangle pathology, as GBA mutation and ApoE4 non-carrier status are both associated with pure DLBD pathology[14-16]. If we are still unable to meet target enrollment then we will include patients of unknown GBA and ApoE genotype. However, these patients will have ApoE genotyping performed in this study, and we will perform post-hoc analysis to see if ApoE4 status affects ^{11}C -PBR28 binding. ApoE testing will be done for research purposes only and results will not be disclosed to subjects. Subjects must have capacity to provide informed consent and consent will be obtained prior to study procedures.

CONFIDENTIAL

This material is the property of Columbia University Medical Center. Do not disclose or use except as authorized in writing by the study sponsor

Screening procedures. Subjects will undergo screening including history, physical examination, routine laboratory studies, neurological examination and brain MRI. Patients meeting clinical criteria for either dementia with Lewy bodies or Parkinson's disease dementia (collectively considered as DLBD) will be included. Diagnosis will be made via consensus conference using clinical criteria[42]. Screening will also include genetic analysis to exclude subjects homozygous for the rs6971 (Ala147Thr) SNP on the TSPO gene. Homozygous subjects have negligible binding on ^{11}C -PBR28 PET imaging and must be excluded; however, heterozygotes may be included[27, 41]. Clinical evaluation will include Montreal Cognitive Assessment (MoCA), Clinical Dementia Rating scale – sum of boxes (CDR-SB), and Unified Parkinson's Disease Rating Scale (UPDRS).

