4.3 Subject Recruitment and Screening

Patients and controls will be recruited from the ADRC, CUMC clinics, and direct referrals. Approximately 50% of enrolled subjects are expected to fail screening procedures or withdraw from the study. We therefore plan to screen 8 subjects in each group to ensure at least 4 in each group complete study procedures. Screening will also include genetic analysis to exclude subjects homozygous for the rs6971 (Ala147Thr) single nucleotide polymorphism on the TSPO gene.

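### Section 7.1 expects significance at an effect size of 1.5 with n = 8, but 4 completers per group are planned, where power is about 43% (two-sided 5% t-test, assumed)

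*Combined protocol and SAP*

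**What the plan says.** Section 7.1 explains that no data exist to power the study accurately. It then borrows an effect size of 1.5 from the earlier Alzheimer's disease study, taken from the regions where patients and controls differed most. If a similar effect is seen, "then we would expect statistically significant differences with sample size of" n = 8. The section does not label the 8 as per group or total, and gives no test, significance level, sidedness or target power.

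The planned numbers are elsewhere:

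- Study Summary, Number of Subjects: "Target enrollment is 8 patients and 8 controls" and "Target accrual is 4 patients and 4 controls".
- Section 3.1: the accrual target is 4 completers in each group.
- Section 4.3: "Approximately 50% of enrolled subjects are expected to fail screening procedures or withdraw from the study", so 8 per group are screened with the aim of securing at least 4 completers per group.

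The sample-size entry in the Study Summary says that "the proposed sample size is not expected to provide enough statistical power to see significant group differences". Section 7.1 neither repeats nor refers to this. Section 7.2 defines the effect size as the mean difference divided by the standard deviation, and plans no group significance test and no confidence interval.

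**The concern.** Section 7.1 is the only justification of sample size in the body of the protocol. A reader who goes straight to the statistical plan learns that significance is to be expected at n = 8 if the effect is 1.5. A reader of the synopsis learns that it is not to be expected. The number 8 matches the enrolled number per group and also the total number of completers (4 + 4), so the sentence can be read in two ways with different statistical consequences.

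The stake is how the pilot is used afterwards. Its stated purpose is "to generate pilot data in patients with DLBD to more effectively design an R01 application", and the effect size is one of its two primary aims. If the size of the study is presented as adequate for significance, and the effect size is reported without an interval, a very imprecise estimate could go into the next study's planning without its uncertainty.

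**Working it through.** **Inputs from the documents.** Effect size d = 1.5 and n = 8 (section 7.1); 4 completers and 8 enrolled per group (Study Summary, sections 3.1 and 4.3); about 50% loss (section 4.3).

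**Assumptions, because the documents state none.** Two-sample t-test with equal groups and alpha 5%. Both sidedness options are shown, because section 2 states a directional hypothesis ("binding will be greater in DLBD patients than controls, with largest differences in temporal and limbic regions") but no one-sided test. The benchmark of 80% power is also assumed.

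**Formulas.** With n per group, df = 2n - 2. For a true effect d, the noncentrality parameter is d × √(n/2), and power is the noncentral-t probability beyond the critical value. For an observed effect d, t = d × √(n/2), referred to the central t distribution.

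**Step 1: the plan's figure, read as 8 analysed per group.** df = 14; noncentrality = 1.5 × √4 = 3.00. Power is 79.7% two-sided and 88.6% one-sided. An observed d of 1.5 gives t = 3.00, p = 0.0096 two-sided. On this reading the figure reproduces.

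**Step 2: the planned design, 4 completers per group (8 in total).** df = 6; noncentrality = 1.5 × √2 = 2.121; two-sided critical value 2.447. An observed d of 1.5 gives t = 2.121.

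| Analysed per group | Power two-sided | Power one-sided | p two-sided, observed d = 1.5 | p one-sided, observed d = 1.5 |
|---|---|---|---|---|
| 4 | 43.0% | 59.1% | 0.078 | 0.039 |
| 8 | 79.7% | 88.6% | 0.0096 | 0.0048 |

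With 4 per group, the smallest observed d that reaches significance is 2.447/√2 = 1.73 two-sided, or 1.37 one-sided. The smallest group size at which an observed d of 1.5 gives two-sided p < 0.05 is 5 (p = 0.045).

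**Step 3: group size for at least 80% power at a true d of 1.5.** Two-sided: 9 per group (84.8%; 8 gives 79.7%). One-sided: 7 per group (84.1%).

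**Step 4: precision.** Inverting the noncentral t for an observed d of 1.5 gives a 95% confidence interval of -0.16 to 3.07 with 4 per group, and 0.36 to 2.60 with 8 per group.

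**Step 5: the completer target in section 4.3.** The expected number of completers is 8 × 0.5 = 4. An expected 4 is not an assured minimum of 4. As an illustration only (independent subjects, same loss rate in both groups, no screening beyond 8), the binomial chance of at least 4 completers among 8 is:

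| Loss | One group | Both groups |
|---|---|---|
| 40% | 83% | 68% |
| 50% | 64% | 41% |
| 60% | 41% | 16% |

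**The case against.** The best defence is that section 7.1 contains no arithmetic error. Read as 8 per group, its figure is right, and it is compatible with the synopsis: 8 analysed per group would be enough, and the 4 planned are not. The sentence is conditional and never says that 8 is the number to be analysed. Section 7.1 opens by calling the study a pilot that cannot be powered accurately, the synopsis admits low power, and no group test is planned. It can also be said that the wording concerns an effect that is seen, so the p-value at an observed 1.5 is the more literal check than power. Finally, a plain t-test leaves out the TSPO genotype correction described in sections 1.1 and 1.4.1.3.

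Much of this is fair and limits the weight of the point, but it does not remove it. If 8 is per group, the section justifies a size that the plan does not expect to analyse and never says so. If 8 is the total, the statement fails two-sided on either check (43.0% power; p = 0.078). It holds one-sided only for an observed effect (p = 0.039), while one-sided power is still 59.1%. The genotype objection stands as a caution about the exact percentage. One covariate that explains no variance lowers df to 5 and two-sided power to about 40%; a covariate that explains variance would raise it. Neither would make 4 per group the design that section 7.1 describes.

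**Conclusion.** The concern holds. Section 7.1 attaches expected significance to a number that is either not the number to be analysed or, at 4 + 4, depends on an unstated one-sided test. It is also not reconciled with the synopsis. At the planned 4 completers per group, a true effect of 1.5 has about 43% power two-sided or 59% one-sided, against about 80% or 89% with 8 per group. These figures rest on an assumed two-sample t-test at 5% without covariates, and on the effect of 1.5, which comes from a different disease and from the regions with the largest differences.

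The consequence is moderate. No planned test, subject number or decision changes, but the text should be corrected. The more important limit at this size is precision, which section 7.1 does not show: an observed effect of 1.5 would be compatible with no difference and with one about twice as large. The promise of at least 4 completers in section 4.3 is a separate, smaller wording point.

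**What to change.** Replace the last sentence of section 7.1 with:

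> With 4 completers per group, a true standardized difference of 1.5 has about 43% power (two-sided 5% two-sample t-test); 9 completers per group would be needed for at least 80% (8 give 79.7%). Significant group differences are therefore not expected; effect sizes will be reported with 95% confidence intervals.

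If a one-sided test was intended, say so and use 59% and 7 per group. If genotype adjustment is intended for the group comparison, say that the quoted power is unadjusted.

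In section 7.2, add 95% confidence intervals for the regional effect sizes. In section 4.3, say that about 4 subjects in each group are expected to complete, in place of the assurance of at least 4. The binomial probabilities above are illustrative and should stay out of the protocol.

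The cost is wording in two sections and one small added calculation, with no extra subjects, visits or procedures. The stated expectation becomes less favourable, but it then agrees with the synopsis.

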7.2 Statistical Methods

Primary outcome

PET images will be analyzed using 1) the two-tissue kinetic model to calculate total distribution volume, corrected for free fraction of radioligand in plasma (V_T/f_p), and 2) the cerebellum as a pseudo-reference region to calculate standardized uptake value ratios (SUVR). Effect size will be calculated for different regions as the difference in means (DLBD vs. controls) divided by the standard deviation.

Secondary outcomes

Coefficient of variation (%COV = standard deviation / mean) will be calculated for controls and patients with DLBD for both V_T/f_p and SUVR data. SUVR values will be calculated using cerebellum as reference regions. Additional reference regions will be explored. Correlation coefficients will be computed to look for correlation between ^{11}C -PBR28 binding (V_T/f_p and SUVR) and clinical severity. Severity will be measured using CDR-sum of boxes, MoCA score, and UPDRS. We will also look for correlations between ^{11}C -PBR28 binding and atrophy, as determined using ROI volumes derived from MRI data.

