These unusual subjects were initially referred to as “non-binders,” reflecting the apparently lack of interaction between ¹¹C-PBR28 and the target protein. In vitro binding assays using peripheral leukocytes isolated from blood samples taken from non-binders showed that these subjects expressed TSPO with ~50-fold lower affinity for ¹¹C-PBR28 than binders[38]. Later binding studies showed that there exist three patterns of ¹¹C-PBR28 binding in human subjects[39, 40]. High affinity binders (HABs) behave as though they express only TSPO that binds with high affinity, low affinity binders (LABs) behave as though they express only TSPO that binds with low affinity, and mixed affinity binders (MABs) behave as though they express both a high- and low-affinity version of TSPO. Genetic studies determined there is a strong association between TSPO binding status and the rs6971 (Ala147Thr) single nucleotide polymorphism on the TSPO gene[29]. HABs lack this polymorphism, LABs are homozygous, and MABs are heterozygous. As the allelic frequency of the polymorphism is 30% based on population studies, 9% are expected to be LABs. Caucasians and African Americans have highest prevalence of the polymorphism while it is rare in Han Chinese and Japanese. Our ex vivo study showed that statistical correction for TSPO genotype improves the ability of ³H-PBR28 to detect differences in TSPO density between controls and patients with schizophrenia in the dorsolateral prefrontal cortex[27]. Therefore, clinical studies have since employed the strategy of excluding LABs and performing statistical correction to remove the effect of systematic physiological differences in ¹¹C-PBR28 binding between HABs and MABs.

1.4.1.4. ¹¹C-PBR28 in Alzheimer’s disease

In our first AD PET study using ¹¹C-PBR28, we found that AD patients had greater binding than MCI patients or controls[41]. The largest differences were seen in parietal and temporal regions. ¹¹C-PBR28 binding correlated with clinical severity, brain atrophy, and earlier age of symptom onset. ¹¹C-PBR28 binding did not conclusively correlate with amyloid burden as measured with ¹¹C-Pittsburgh Compound B. This study used arterial blood sampling to calculate total distribution volume using the two-tissue compartment model, with correction for free fraction of radioligand. Even after TSPO genotype correction, variance of the PET data was relatively large (coefficient of variance = 34 - 73%).

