Image analysis. PET images will be analyzed using two methods. First, kinetic analysis will be performed using PMOD software (PMOD Technologies). Subject MR images will be coregistered to native space PET images and then segmented to define gray matter regions of interest (ROIs): prefrontal cortex, combined superior and inferior parietal lobule, occipital cortex, inferior temporal cortex, combined middle and superior temporal cortex, hippocampus, parahippocampal gyrus, anterior cingulate, amygdala, insula, and cerebellum. These regions have been selected based on where the largest number of Lewy bodies have been previously reported[45]. The two-tissue kinetic model using time-activity curves from each ROI and the metabolite-corrected arterial input function will be used to calculate total distribution volume, corrected for free fraction of radioligand in plasma (V_T/f_p). Second, the cerebellum will be used as a pseudo-reference region to calculate standardized uptake value ratios (SUVR) for each target ROI. To determine the best time interval for non-invasive measurement of TSPO binding in DLBD, we will calculate SUVR using different time intervals and compute correlation coefficients with the gold-standard measurement V_T/f_p . The time intervals that correspond to SUVR values that have strongest correlation with V_T/f_p will be used to calculate SUVR for the group comparisons between patients with DLBD and controls.

Statistical analysis.

Primary outcome

PET images will be analyzed using 1) the two-tissue kinetic model to calculate total distribution volume, corrected for free fraction of radioligand in plasma (V_T/f_p), and 2) the cerebellum as a pseudo-reference region to calculate standardized uptake value ratios (SUVR). Effect size will be

calculated for different regions as the difference in means (DLBD vs. controls) divided by the standard deviation.

Secondary outcomes

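### The primary V_T/f_P effect size has no TSPO genotype term, although the protocol relies on genotype correction to admit heterozygotes

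*Combined protocol and SAP*

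**What the plan says.** The same primary formula stands in the Study Summary, section 3.1 and section 7.2. In 7.2 it reads "Effect size will be calculated for different regions as the difference in means (DLBD vs. controls) divided by the standard deviation"; in 3.1, "calculated for different regions as the difference in means (DLBD vs. controls) divided by the standard deviation". It applies by region to V_T/f_P and SUVR. None of the three places has a genotype covariate, stratification, matching or genotype-specific scaling.

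The background takes a different position. Section 1.1 states: "Statistical correction for TSPO genotype allows inclusion of individual heterozygous for the polymorphism". Section 1.4.1.3 reports: "Our ex vivo study showed that statistical correction for TSPO genotype improves the ability of" the tritiated ligand to separate schizophrenia patients from controls. It then describes the practice of clinical studies since: drop LABs and also correct, "performing statistical correction to remove the effect of systematic physiological differences in" binding between HABs and MABs.

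Of these two steps the plan adopts only the first. Sections 3.1 and 4.2 exclude homozygotes, and 3.1 admits heterozygotes. The one genotype analysis planned is a post-hoc look at ApoE4, which is another gene (section 3.1).

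The purpose is given in section 1.1, to "generate pilot data in patients with DLBD to more effectively design an R01 application", and in the Study Summary: "This is a Phase 2 pilot study to determine feasibility and preliminary data for a larger study".

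**The concern.** The protocol treats the HAB/MAB difference as systematic and as the reason correction is needed, then specifies a formula that ignores it. An analyst who follows 7.2 would not correct.

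Three things are at stake.

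- **The effect size.** Over repeated samples the raw difference in means is unbiased with respect to genotype, because either group may draw more MABs. But the pilot yields one sample. Its V_T/f_P effect sizes carry whatever imbalance occurs, and in principle all regions move together. No planned output gives HAB and MAB counts by group, so a reader could not see it.
- **The SD.** The planned denominator includes variance between HABs and MABs. This lowers the standardized difference on average, and it is not the SD that a genotype-corrected larger study would have.
- **The %COV.** Section 1.4.1.4 gives 34-73% for the earlier Alzheimer's study after genotype correction. The pilot's uncorrected %COV is not on that scale.

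**Working it through.** **Inputs from the documents.** Allele frequency 0.30 (1.4.1.3); 4 completers per group (3.1); COV 34-73% after genotype correction (1.4.1.4); effect size 1.5 (7.1), used as the true within-genotype value in the simulation.

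**Assumption not in the documents.** MAB binding is a fraction r = 0.10 to 0.50 below HAB binding. The COV of 34-73% is taken as the within-genotype COV here.

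**1. The protocol's own figure.** "As the allelic frequency of the polymorphism is 30% based on population studies, 9% are expected to be LABs". Check: 0.30² = 0.09, so it reproduces. MAB = 2 × 0.30 × 0.70 = 0.42 and HAB = 0.70² = 0.49.

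**2. MAB share among eligible subjects.** p = 0.42 / (0.42 + 0.49) = 0.42/0.91 = 0.462.

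**3. Imbalance, 4 v 4.** With two independent Binomial(4, 0.462) counts:

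- equal: 0.274
- differ by one: 0.438
- differ by two or more: 1 − 0.274 − 0.438 ≈ 0.287
- unequal: 1 − 0.274 = 0.726

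At an allele frequency of 0.20, p = 0.333, unequal 0.707, two or more 0.256.

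**4. Gap in within-genotype SDs.** g = r / [COV × (1 − p·r)].

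- Low: 0.10 / [0.73 × (1 − 0.046)] = 0.14
- Middle: 0.30 / [0.50 × (1 − 0.138)] = 0.70
- High: 0.50 / [0.34 × (1 − 0.231)] = 1.91

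**5. Variance ratio and shift.** Total over within-genotype variance is 1 + p(1−p)g². A k-subject imbalance shifts the effect size by (k/4)·g / √(1 + p(1−p)g²). For k = 2:

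| g | Variance ratio | Shift |
|---|---|---|
| 0.14 | 1.005 | 0.07 |
| 0.70 | 1.12 | 0.33 |
| 1.91 | 1.91 | 0.69 |

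The last row needs the largest gap and the smallest COV together.

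**6. Simulation.** 200,000 samples per gap, normal errors, true within-genotype effect size 1.5, pooled SD. Samples where genotype could not be estimated were dropped. Repeat runs agree to within about 0.02.

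| g | Median raw d, patients +2 MABs | Median raw d, patients −2 MABs | RMSE raw | RMSE adjusted |
|---|---|---|---|---|
| 0.14 | 1.49 | 1.63 | 1.09 | 1.29 |
| 0.70 | 1.15 | 1.85 | 1.05 | 1.29 |
| 1.00 | 0.95 | 1.90 | 1.02 | 1.28 |
| 1.91 | 0.41 | 1.91 | 0.99 | 1.28 |

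The adjusted median stays at 1.57-1.60 whatever the imbalance. The model's residual variance averages 1.00 at every gap, so it recovers the within-genotype variance. But raw d has the lower overall RMSE throughout.

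**7. Intervals for an observed value of 1.5 (noncentral t).**

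- Raw, 6 df, factor √(1/4 + 1/4) = 0.707: −0.16 to 3.07
- Adjusted, 5 df, 2 v 2 MABs, same factor: −0.20 to 3.11
- Adjusted, 5 df, 3 v 1 MABs, factor √(0.5 + 0.5²/1.5) = 0.816: −0.39 to 3.28

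**8. Inestimable genotype term.** Confounded with group 0.0076 + all one genotype 0.0091 = 0.017 (0.044 at an allele frequency of 0.20).

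**The case against.** The strongest case is that adjustment does not improve the estimate. The raw difference is unbiased, the adjusted d has higher RMSE at every gap, and it is the closer of the two to 1.5 in only 46-49% of samples for gaps of 0.14 to 1.0 SD (53% at 1.91). Ordinary sampling error at 4 v 4 exceeds any genotype shift, the Study Summary disclaims power, and the gap is assumed. That stands. It is why the raw value should remain the headline and the adjusted one should be a companion.

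It can also be said that correction is implied, because 3.1 cites the genotype-corrected work when it admits heterozygotes, and that counts might appear in a baseline table anyway. The first does not survive an explicit formula stated three times without genotype. The second is possible, but the plan does not say so. Counts alone would show an imbalance; they would not give the variance a corrected study needs.

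Three smaller points stand. Effect sizes are planned for several regions and two measures, and this concern is about V_T/f_P. The protocol plans no comparison of %COV with the earlier 34-73%, so an extra %COV is needed only if that comparison is made. And if the variant is rarer among those recruited, the genotype term fails more often: at an allele frequency of 10% it is inestimable in 20% of samples, and an imbalance of two or more falls to 15%. The fix therefore needs a fallback.

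**Conclusion.** The concern holds and should be fixed. The primary analysis omits the correction on which the protocol's own rationale for enrolling heterozygotes rests.

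The chance of imbalance, 73% for any and 29% for two or more subjects, rests only on the stated allele frequency, Hardy-Weinberg proportions and 4 independent completers per group. The size of the shift, 0.07 to 0.69 for a two-subject imbalance, rests on the assumed 10-50% gap. At the low end the problem is small; in the middle case (0.7 SD) the median raw value is 1.15 or 1.85 according to which group has two more MABs. The planned variance exceeds the within-genotype variance by a factor of 1.005 to 1.91 over the same range.

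The gain from correction is a value not moved by the genotype mix and a variance on the scale of a corrected larger study. It is not greater accuracy of the pilot effect size.

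**What to change.** In section 7.2, section 3.1 and the Study Summary, keep the unadjusted effect size as the headline value and add:

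> For V_T/f_P in each region, a linear model with group and TSPO genotype (HAB/MAB) will also be fitted across all completers. The companion estimate is the group coefficient divided by the residual SD (5 residual df). Both effect sizes are reported with 95% noncentral-t intervals and with HAB and MAB counts per group. The companion does not replace the unadjusted value. The genotype-adjusted residual SD, with its interval, is the variance carried to a larger study that will correct for genotype. If genotype cannot be estimated, only the unadjusted value is reported and this is stated.

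Keep the per-group %COV as planned. For any comparison with the earlier 34-73%, add one %COV that uses the 5-df residual SD over the group mean adjusted to a named genotype: HAB, or the one used in the earlier Alzheimer's analysis, which the documents do not state. For SUVR, treat genotype adjustment as a sensitivity analysis only.

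**Cost.** Wording only: section 6 already provides for TSPO genotyping at screening. One of 6 df is spent. The adjusted d is noisier and averages 1.78 for a true 1.5. Its residual SD is itself imprecise, with a 95% interval of 0.62 to 2.45 times the estimate on 5 df. There is about a 1.7% chance that only the unadjusted value can be reported (4% at an allele frequency of 20%).
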